## 5.2. Handling of Dropouts, Missing Data, and Outliers

### 5.2.1. Handling of Missing Efficacy Data

Tender (and swollen) joint count will be the sum of the joints where tenderness (or swelling) is marked as Present on the CRF. A missing response will be treated the same as an Absent response, in that, it will not contribute to the joint count.

Subjects with missing efficacy assessments will be imputed as non-responders (non-response imputation or NRI) for dichotomous endpoints. Subjects with a missing component of a composite endpoint will be imputed as non-responders for that component. The subject may therefore be a responder to the endpoint, if the subject met a sufficient number of criteria from other components.

Subjects missing one or more components of composite endpoints will be included, illustrated for the primary endpoint, ACR50, as follows:

Situation	ACR50 result
If both SJC66 and TJC68 have reductions $\geq 50\%$ : 
 
- If at least 3 of the other 5 components have reductions <math>\geq 50\%</math>, irrespective of missing/available on the others
 
- If at least 3 of the other 5 components have a reduction of <math>< 50\%</math>, irrespective of missing/available on the others
 
- All other situations
 
	
Responder
 
Non-responder
 
Missing

If result is available on both of SJC66 and TJC68, and at least one has $<50\%$ : 
 
- Irrespective of results or missingness on the other 5 components
 
	Non-responder
If one of SJC66 and TJC68 is missing, and the other has reduction $\geq 50\%$ : 
 
- If at least 3 of the other 5 components have reductions <math>\geq 50\%</math>, irrespective of missing/available on the others
 
- If at least 3 of the other 5 components have a reduction of <math>< 50\%</math>, irrespective of missing/available on the others
 
- All other situations
 
	
Missing
 
Non-responder
 
Missing

If one of SJC66 and TJC68 is missing, and the other has reduction $<50\%$ : 
 
- Irrespective of results or missingness on the other 5 components
 
	Non-responder

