### 6.6.1. Primary Efficacy Analysis

The primary efficacy variable is defined as ACR50, the proportion of subjects achieving 50% improvement in ACR core set measurements.

The statistical null and alternative hypotheses to be used to assess the primary objective are:

$$H_0: \pi_{ABY} - \pi_{PBO} = 0$$

$$H_A: \pi_{ABY} - \pi_{PBO} \neq 0$$

where  $\pi_{ABY}$  and  $\pi_{PBO}$  are the proportion of subjects achieving ACR50 at Week 16 among subjects randomly assigned to receive izokibep and placebo, respectively. One set of hypotheses will be tested for each dose frequency of izokibep (QW and Q2W).

The treatment strategy approach for the estimand will be used in general, so subjects will be included using observed data at Week 16 regardless of treatment discontinuation, concomitant medication, protocol deviations, or other actions. Subjects with missing ACR50 assessments at Week 16 will be imputed as non-responders (non-response imputation or NRI).

Three components of the primary endpoint (subject's assessment of pain, subject's global assessment of disease activity, and investigator's global assessment of disease activity) were assessed using a visual analog scale (VAS), consisting of a horizontal line, 100 mm in length, with anchor statements at either end. The subject or investigator was asked to place a single vertical line through the VAS at the point that best corresponds to assessment. At some sites, and for some subjects, the VAS was not administered as intended. If a line was not 100 mm in length, the score used for analysis was calculated as  $100 \times (\text{distance from left to mark}) / (\text{total length of horizontal line})$ . If the subject was requested to write a number or was verbally asked for a number, that value will be used for analysis. Such protocol deviations will be noted in listings, and sensitivity analyses will be reported to assess the impact of such deviations. A spreadsheet will be created, after database lock and before unblinding, to note which subjects answered questions using a different length line, or by writing or verbally responding with a number. This spreadsheet will be signed and dated, and entered into the study files, before database lock to verify the protocol deviations and sensitivity analyses defined below.

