status from the imputed values. Predictors in the regression model for missing values at Week 2 will be the randomization stratification factors of prior TNFi use, and LEI>0/LEI=0, as well as sex (male/female), race (white/non-white), age (continuous), and BMI (continuous). For each of the 7 components, baseline value will be included as a continuous predictor. Predictors in the regression model for missing values after Week 2 will be all of these variables, plus the value of the component being predicted at all prior scheduled assessments. Missing ACR50 values in both the placebo group and three izokibep groups will be imputed using observed data from the placebo group only. Data will be processed sequentially by repeatedly calling SAS® PROC MI to impute missing outcomes. A total of 100 imputations will be imputed to form the complete data set with a pre-specified seed (6848251) to ensure reproducibility. These multiple imputed data sets are then analyzed by using the same method for the primary analysis for complete data as specified in Section 6.6.1. The final inference on treatment difference is conducted from the multiple datasets using Rubin's combining rules. Other imputation, fully conditional specification method may be implemented if the multiple imputation model does not converge. Sample SAS code:

```
proc mi n impute=100 seed=6848251;
  var acr50;
  ods select misspattern;
run;
```

**VAS Supplemental Analyses:** A supplemental primary analysis using the VAS data on a scale from 0 to 100 mm will be performed in order to evaluate the robustness of the results when variations in the collection of the VAS data were reported by the investigator. The impact of VAS collection on paper (single vertical line through the VAS at the point that best corresponds to their feeling of pain), VAS collection via verbal response from the subject, and VAS scales that measured 100 mm will be examined by conducting the following analyses:

- Using only VAS data collected on a 0 to 100 scale (paper or verbal), excluding data collected on a 0 to 10 scale.
- Using only VAS data collected on a 0 to 100 horizontal line (paper only), excluding data collected verbally.
- Using only VAS data collected on a 0 to 100 scale (paper only, with line that measured 100 mm), excluding those collected with lines of a different length (0 to 10, 0 to <100mm, 0 to >100mm), excluding data collected verbally.

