If there are no subjects who meet one of the protocol deviation criteria (data collected on a 0 to 10 scale, data collected verbally, or data collected using a line not 100 mm) then the corresponding subgroup analysis above will be omitted.

**Q2W and Q4W Supplemental Analyses:** A supplemental analysis is planned for subjects who were randomized to receive izokibep Q2W or izokibep Q4W. The analysis of subjects randomized to receive izokibep Q2W will group subjects according to the longest number of consecutive doses of izokibep or placebo that were received within the first 16 weeks of treatment of Period 1:

- Did not receive consecutive doses of izokibep or placebo
- Received consecutive doses, but no more than two consecutive doses of either izokibep or placebo
- Received at least three consecutive doses of izokibep or placebo, but not four consecutive doses.
- Received four or more consecutive doses of izokibep or placebo.

Because the number of subjects in the first group who did not receive consecutive doses of izokibep or placebo is expected to be small, the first two groups will be combined. The primary analysis will be run in each of the resulting three subsets of subjects, comparing each subset of subjects to the entire group of placebo subjects. Subjects will be classified according to doses actually received (not assigned), and included only if the subjects receive at least 8 total doses (izokibep or placebo) and have an assessment after the 8th dose (with other subjects excluded from this supplemental analysis). Informal comparisons of the resulting analyses (p-values, point estimates and treatment differences) will be used to assess whether the three subsets of subjects, with different PK characteristics, have similar responses.

All subjects who were randomized to receive Q2W and who received correct treatment at each administration until week 12 (or until discontinuation of study drug, whichever came first) will be summarized with week 12. The number and proportion of subjects achieving ACR50, as an additional supplemental analysis to understand the impact of dosing errors.

An analogous analysis of subjects who were randomized to receive izokibep Q4W will also be reported. This will classify such subjects into two subsets:

- Received no more than four consecutive doses of placebo
- Received more than four consecutive doses of placebo.

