#### 6.6.4. Supplementary Analyses for the Secondary Efficacy Analysis

Sensitivity analyses will use analysis of covariance on change in physical function of HAQ-DI from baseline to Week 16, with stratification variables used for randomization also included as covariates, along with baseline physical function of HAQ-DI.

Sensitivity analysis for physical function of HAQ-DI will also use multiple imputations. Physical function of HAQ-DI missing as Week 16 will be replaced with the imputed value from the imputation dataset. The imputation dataset will be created from the placebo subjects who have complete data.

**Multiple Imputation:** Multiple imputations will be implemented to replace missing endpoint data using multiple draws from a posterior predictive distribution estimated from the placebo group only. For HAQ-DI at Week 2, 4, 12, and 16, assuming monotone missingness

pattern, missing HAQ-DI will be imputed using previous HAQ-DI (except for Week 2) up to the time point of interest and randomization strata using placebo group only. Missing HAQ-DI in the placebo group and two izokibep groups will be imputed. Monotonicity in missing data will first be imputed with MCMC. The resulting data will then be processed sequentially by repeatedly calling SAS® PROC MI to impute missing outcomes. A total of 100 imputations will be imputed to form the complete data set with a pre-specified seed (36767) to ensure reproducibility. These multiple imputed data sets will then be analyzed by using the same method for the HAQ-DI endpoint analysis as specified in Section 6.6.3. The final inference on treatment difference is conducted from the multiple datasets using Rubin's combining rules. Other imputation, fully conditional specification method may be implemented if the multiple imputation model does not converge.

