**Appendix 2.4 Disease Activity Score in 28 joints-C-reactive protein (DAS28-CRP)**

The DAS28-CRP considers 28 tender and swollen joint counts, general health (subject's global assessment of disease activity (SGADA) using a 100 mm visual analogue scale (VAS) with 0=best, 100=worst), plus levels of an acute phase reactant (CRP (mg/L)).

DAS28 values were calculated as follows:

$$\text{DAS28-CRP} = 0.56 * \sqrt{(\text{TJC28})} + 0.28 * \sqrt{(\text{SJC28})} + 0.014 * \text{SGADA} + 0.36 * \ln(\text{CRP}+1) + 0.96;$$

where TJC=tender joint count and SJC=swollen joint count;

SGADA = subject's global assessment of disease activity on a 0-100 VAS.

If one or more components are missing in the formula, then DAS28-CRP is set to be missing.

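### SAP 6.6.1 uses written or verbal VAS numbers as given, with no conversion from 0-10: such a Week 16 answer always passes the MDA pain or global cut-off, and a scale switch distorts ACR20/ACR50

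*SAP*

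**What the plan says.** SAP 6.6.1 reports that the VAS was not always administered as intended for three ACR components: subject's pain, subject's global and investigator's global assessment. It gives two rules. A mark on a line that is not 100 mm long is rescaled to 0-100 by the ratio of mark distance to line length. For numeric answers the rule is: "If the subject was requested to write a number or was verbally asked for a number, that value will be used for analysis". A spreadsheet is to be prepared "to note which subjects answered questions using a different length line, or by writing or verbally responding with a number"; recording the scale of the number is not mentioned.

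SAP 6.6.2 plans three supplemental VAS analyses of the primary endpoint. The first is "Using only VAS data collected on a 0 to 100 scale (paper or verbal), excluding data collected on a 0 to 10 scale". The third works by "excluding those collected with lines of a different length (0 to 10", among other lengths. An analysis is dropped if no subject meets the corresponding deviation: "data collected on a 0 to 10 scale, data collected verbally, or data collected using a line not 100 mm".

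For secondary endpoints, SAP 6.6.4 covers HAQ-DI only: "Sensitivity analyses will use analysis of covariance on change in physical function of HAQ-DI from baseline to Week 16", plus multiple imputation for the same endpoint. SAP 5.2.1 states: "Subjects with a missing component of a composite endpoint will be imputed as non-responders for that component". The scoring appendices presuppose a 0-100 score; Appendix 2.4, for example, defines the "global assessment of disease activity on a 0-100 VAS".

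**The concern.** The intended score is plainly 0-100, but the rule for numeric answers contains no step that produces one. Section 6.6.2 treats a 0-10 scale as a deviation distinct from verbal collection and from line length, and removes such data only in a supplemental analysis. Any that exist therefore stay in the main analysis, unconverted.

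MDA is the most exposed endpoint because its pain and global criteria are absolute cut-offs. ACR20 and ACR50 use percentage change from baseline, so they are distorted only if a subject's scale differs between baseline and Week 16. DAPSA, cDAPSA, DAS28-CRP and PASDAS are understated at any affected visit.

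Three further gaps follow. The numeric rule names only the subject, so a number given by an investigator has no rule. MDA and ACR20 are alpha-controlled but have no VAS sensitivity analysis. And 6.6.2 does not say whether excluding data makes the component missing, hence non-response for that component under 5.2.1, or drops the subject.

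**Working it through.** The plan gives no figure for this issue, so there is none to reproduce. Everything below is per affected subject. B and W are the true baseline and Week 16 values on 0-100.

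**MDA** (Protocol 8.1.1.5, SAP Appendix 2.11: 5 of 7 criteria; pain ≤ 15 mm, global ≤ 20 mm)
- The largest 0-10 answer is 10, below both cut-offs. All 11 integer answers (0 to 10) pass each criterion.
- After multiplying by 10, only 0 and 1 pass for pain (2 of 11), and only 0, 1 and 2 pass for global (3 of 11).
- Both items affected: 5 − 2 = 3 of the remaining 5 criteria suffice. One item affected: 5 − 1 = 4 of the remaining 6.
- Illustration, assuming independent criteria each met with the same probability p:

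| p | No item automatic | One automatic | Two automatic |
|---|---|---|---|
| 0.3 | 2.9% | 7.0% | 16.3% |
| 0.5 | 22.7% | 34.4% | 50.0% |

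**ACR components** (SAP 2.4: percentage reduction from baseline)
- Baseline on 0-100, Week 16 on 0-10: scored reduction = 1 − (W/10)/B = 1 − W/(10B).
  - No true change, W = B: 1 − 1/10 = 90%.
  - Worst answer, W = 100, entered as 10: the 50% threshold is met if 10/B ≤ 0.5, so B ≥ 20 mm; the 20% threshold is met if 10/B ≤ 0.8, so B ≥ 12.5 mm.
- Baseline on 0-10, Week 16 on 0-100: scored reduction = 1 − W/(B/10) = 1 − 10W/B.
  - A 50% score needs W ≤ 0.05B, a true reduction of at least 95%; a 20% score needs W ≤ 0.08B, a true reduction of at least 92%.
  - Example: baseline answer 7, Week 16 mark 20 mm. Scored: (7 − 20)/7 = −186%. True: (70 − 20)/70 = 71% reduction.
- Same scale at both visits: the factor of 10 cancels. An answer going from 7 to 3.5 and a mark going from 70 to 35 mm are both 50%.

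**Composite scores** (SAP Appendices 2.4 to 2.6; true 70 entered as 7)
- DAPSA and cDAPSA: (70 + 70)/10 − (7 + 7)/10 = 14.0 − 1.4 = 12.6, against a low-disease-activity cut-off of 14. One item only: 7.0 − 0.7 = 6.3.
- DAS28-CRP: 0.014 × (70 − 7) = 0.88.
- PASDAS through the subject's global: 0.159 × (√70 − √7) = 0.91 as the formula is printed; 0.91 × 1.5 = 1.36 if the factor 1.5 applies to the whole sum.

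**Place in the testing sequence** (SAP 6.6)
- 7 QW tests + 7 Q2W tests = 14. ACR50, MDA and ACR20 are tests 1, 4 and 5 for QW and 8, 11 and 12 for Q2W: 6 of 14.
- MDA for QW is test 4, so the 14 − 4 = 10 later tests depend on it.

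**The case against.** The strongest reply is that the affected data may not exist. Section 6.6.1 mentions numbers but no 0-10 scale; the first supplemental analysis pairs verbal answers with 0-100; and the third lists 0 to 10 among line lengths, which the rescaling rule already covers. A conversion could also be built into the eCRF or its completion guidelines, which are not available here. Every scoring definition presupposes 0-100, so a literal 7 would contradict the plan's own intent.

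This stands as a limit on size. It does not remove the gap: the list of deviations in 6.6.2 separates a 0-10 scale from verbal collection and from line length, and no text in either document supplies the conversion.

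It is also fair that the ACR effect needs a scale switch that no text reports, that both joint-count criteria must still be met, and that ACR50 has three supplemental analyses. Without a switch, only MDA is exposed among the alpha-controlled endpoints, which is 2 of the 14 tests. Collection was double-blind and nothing suggests that the deviation differs by arm, so no inflation of type I error is shown.

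**Conclusion.** The rule is wrong as written and should be fixed before unblinding. The absence of a conversion step, and the arithmetic for each affected answer, are certain. The consequence is conditional: if written or verbal 0-10 answers were entered unconverted, MDA responders are misclassified, and with a within-subject scale switch ACR20 and ACR50 responders can be too. A number given on a 0-100 scale is unaffected.

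The number of affected subjects, the direction of any effect on the treatment difference and any effect on power cannot be determined from the documents, and no figure is claimed for them.

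**What to change.** Replace the numeric-answer sentence in SAP 6.6.1 with a rule to this effect: written or verbal answers on a 0-10 scale are multiplied by 10; answers on a 0-100 scale are used as recorded; if the scale cannot be established before unblinding, the component is set to missing. In addition:

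- Apply the rule to subject and investigator answers alike, before deriving ACR, MDA/VLDA, DAPSA/cDAPSA, DAS28-CRP and PASDAS.
- State that the spreadsheet records the number scale per item and visit. Its timing also needs reconciling: 6.6.1 has it created after database lock but signed before it.
- Keep the three VAS analyses in 6.6.2 as sensitivity analyses, extend them to MDA and ACR20, and state whether an excluded value is a missing component or an omitted subject.

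The cost is one SAP sentence, one spreadsheet field (the first supplemental analysis needs the scale anyway), one derivation step and reruns of planned analyses for two endpoints. If no 0-10 answers exist, the conversion changes nothing. The downside is an assumption that a number times 10 is comparable with a VAS mark, and that an answer of unknown scale counts as non-response for that component under 5.2.1.

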## 6.6.2. Supplementary Analyses for the Primary Efficacy Analysis

**Tipping point analysis:** A tipping point analysis will be performed in order to evaluate the robustness of the results of the primary analysis. This analysis will use simulations to assess the impact of different response rates in subjects with missing primary endpoint data, and how different the response rates must be to change the conclusions of the study. The tipping point analysis will impute mean response rates in the two groups. Imputed response rates will be based on the response rates among subjects with observed primary endpoint data at Week 16. Sets of imputed mean response rates will include the observed response rates ( $\hat{\pi}_{ABY}$ ,  $\hat{\pi}_{PBO}$ ), as observed in each stratum, and rates that differ in increments of  $\pm 0.02$ , adjusted independently in each arm. For each of the 121 imputed mean response rates ( $\hat{\pi}_{ABY} + a$ ,  $\hat{\pi}_{PBO} + b$ ), with  $a$  and  $b$  each taking on all values from  $-0.10$  to  $+0.10$  in increments of  $0.02$ , 1000 simulations will be reported. Within each simulation, a random number mechanism will be used to assign each subject who is missing the primary endpoint at Week 16 to either response or non-response. The primary stratified analysis will be reported on each simulation, and the probability that the null hypothesis of equal response rates is rejected will be reported for each set of imputed response rates. A graphical output will summarize the rejection probability for various sets of response rates. The same tipping point analysis will be performed in comparing each izokibep group to placebo.

**Multiple Imputation:** Multiple imputation using a Markov chain Monte Carlo (MCMC) technique will be implemented to replace missing endpoint data using multiple draws from a posterior predictive distribution estimated from the placebo group only. For ACR50, assuming monotone missingness pattern, missing ACR50 at Weeks 2, 4, 12 and 16 will be imputed by first imputing the 7 components of the ACR50 criteria (SJC66, TJC68, subject's VAS assessment of pain, SGADA, IGADA, HAQ-DI, and CRP), then assigning ACR50

status from the imputed values. Predictors in the regression model for missing values at Week 2 will be the randomization stratification factors of prior TNFi use, and LEI>0/LEI=0, as well as sex (male/female), race (white/non-white), age (continuous), and BMI (continuous). For each of the 7 components, baseline value will be included as a continuous predictor. Predictors in the regression model for missing values after Week 2 will be all of these variables, plus the value of the component being predicted at all prior scheduled assessments. Missing ACR50 values in both the placebo group and three izokibep groups will be imputed using observed data from the placebo group only. Data will be processed sequentially by repeatedly calling SAS® PROC MI to impute missing outcomes. A total of 100 imputations will be imputed to form the complete data set with a pre-specified seed (6848251) to ensure reproducibility. These multiple imputed data sets are then analyzed by using the same method for the primary analysis for complete data as specified in Section 6.6.1. The final inference on treatment difference is conducted from the multiple datasets using Rubin's combining rules. Other imputation, fully conditional specification method may be implemented if the multiple imputation model does not converge. Sample SAS code:

```
proc mi n impute=100 seed=6848251;
  var acr50;
  ods select misspattern;
run;
```

**VAS Supplemental Analyses:** A supplemental primary analysis using the VAS data on a scale from 0 to 100 mm will be performed in order to evaluate the robustness of the results when variations in the collection of the VAS data were reported by the investigator. The impact of VAS collection on paper (single vertical line through the VAS at the point that best corresponds to their feeling of pain), VAS collection via verbal response from the subject, and VAS scales that measured 100 mm will be examined by conducting the following analyses:

- Using only VAS data collected on a 0 to 100 scale (paper or verbal), excluding data collected on a 0 to 10 scale.
- Using only VAS data collected on a 0 to 100 horizontal line (paper only), excluding data collected verbally.
- Using only VAS data collected on a 0 to 100 scale (paper only, with line that measured 100 mm), excluding those collected with lines of a different length (0 to 10, 0 to <100mm, 0 to >100mm), excluding data collected verbally.

If there are no subjects who meet one of the protocol deviation criteria (data collected on a 0 to 10 scale, data collected verbally, or data collected using a line not 100 mm) then the corresponding subgroup analysis above will be omitted.

**Q2W and Q4W Supplemental Analyses:** A supplemental analysis is planned for subjects who were randomized to receive izokibep Q2W or izokibep Q4W. The analysis of subjects randomized to receive izokibep Q2W will group subjects according to the longest number of consecutive doses of izokibep or placebo that were received within the first 16 weeks of treatment of Period 1:

- Did not receive consecutive doses of izokibep or placebo
- Received consecutive doses, but no more than two consecutive doses of either izokibep or placebo
- Received at least three consecutive doses of izokibep or placebo, but not four consecutive doses.
- Received four or more consecutive doses of izokibep or placebo.

Because the number of subjects in the first group who did not receive consecutive doses of izokibep or placebo is expected to be small, the first two groups will be combined. The primary analysis will be run in each of the resulting three subsets of subjects, comparing each subset of subjects to the entire group of placebo subjects. Subjects will be classified according to doses actually received (not assigned), and included only if the subjects receive at least 8 total doses (izokibep or placebo) and have an assessment after the 8th dose (with other subjects excluded from this supplemental analysis). Informal comparisons of the resulting analyses (p-values, point estimates and treatment differences) will be used to assess whether the three subsets of subjects, with different PK characteristics, have similar responses.

All subjects who were randomized to receive Q2W and who received correct treatment at each administration until week 12 (or until discontinuation of study drug, whichever came first) will be summarized with week 12. The number and proportion of subjects achieving ACR50, as an additional supplemental analysis to understand the impact of dosing errors.

An analogous analysis of subjects who were randomized to receive izokibep Q4W will also be reported. This will classify such subjects into two subsets:

- Received no more than four consecutive doses of placebo
- Received more than four consecutive doses of placebo.

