### 2.3. Sample Size and Power

Response rates for ACR50 are expected to be 20% for placebo and 45% for a dose regimen of 160 mg izokibep (QW or Q2W or both). With 100 subjects receiving placebo and 100 subjects receiving a dose regimen of 160 mg izokibep, there will be 97% power to show a difference in the primary endpoint of ACR50 response rate. If a 45% response rate is observed with a dose regimen of izokibep, the 2-sided 95% confidence interval for the true response rate will have a half-width of approximately 10 percentage points.

Up to 60% of subjects are expected to have enthesitis at baseline, based on the LEI. Response rates, proportion of subjects who have LEI = 0 at Week 16, are expected to be 25% for placebo and 60% for subjects receiving izokibep. With 50 subjects with enthesitis at baseline receiving placebo and 50 subjects receiving a dose regimen of izokibep, there will be 95% power to show a difference in the secondary endpoint of resolution of enthesitis. A lower rate of enthesitis at baseline will result in a lower power, but power will be at least 80% with the same assumptions on response rate, if 30 subjects with enthesitis at baseline receive placebo and 30 subjects receive a dose regimen of izokibep.

With 25 subjects receiving izokibep 80 mg Q4W, the 2-sided 95% confidence interval for the true response rate will have a half-width of up to approximately 20 percentage points.

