### 2.4. Primary Efficacy Variable

The primary efficacy variable for the study is the ACR50 response rate, defined as the proportion of subjects who achieve a 50% improvement from baseline in ACR core set measurements. The primary timepoint for analysis is Week 16.

ACR50 criteria require that the subject experiences an improvement in the following parameters compared to baseline:

- $\geq 50\%$  reduction in 68 Tender Joint Count (TJC68)
- $\geq 50\%$  reduction in 66 Swollen Joint Count (SJC66)
- $\geq 50\%$  reduction in 3 of 5 additional measures:
  - Subject's Assessment of Pain (SAPVAS)
  - Subject's Global Assessment of Disease Activity (SGADA)
  - Investigator's Global Assessment of Disease Activity (IGADA)
  - HAQ-DI
  - Acute phase reactant (C-reactive protein [CRP])

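### The supplementary ACR50 multiple imputation leaves out every other component's post-baseline values, so it weakens the correlation between components and understates imputed ACR50

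*SAP*

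**What the plan says.** SAP 6.6.2 (Multiple Imputation) says that missing ACR50 at Weeks 2, 4, 12 and 16 is "imputed by first imputing the 7 components of the ACR50 criteria", with ACR50 then assigned from the imputed values. The predictors are listed:

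- **Week 2:** "Predictors in the regression model for missing values at Week 2 will be the randomization stratification factors of prior TNFi use" and baseline enthesitis, with sex, race, age and BMI.
- **Baseline:** "For each of the 7 components, baseline value will be included as a continuous predictor". This can mean the component's own baseline, or all seven baselines in every model.
- **After Week 2:** all of these, "plus the value of the component being predicted at all prior scheduled assessments".

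Missing values in all arms "will be imputed using observed data from the placebo group only". The section names MCMC, but says the data are processed sequentially by repeated PROC MI calls. The sample code has `var acr50` as its only variable and no component. The fallback is "Other imputation, fully conditional specification method may be implemented if the multiple imputation model does not converge", with no predictor list.

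SAP 2.4 defines ACR50 as at least 50% reduction in TJC68 and in SJC66, plus at least 50% "reduction in 3 of 5 additional measures".

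**The concern.** ACR50 is a joint event: two joint counts and three of five other measures must improve in the same subject at the same visit. How often that happens depends on how strongly the components move together. The listed models carry no post-baseline information from one component to another, so the imputation residuals are independent across the seven components. Each component can have the right marginal distribution while the coincidence that defines response is too rare.

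This analysis has a distinct job. The primary analysis (SAP 6.6.1) sets missing ACR50 to non-response. The tipping-point grid in SAP 6.6.2 moves each arm's rate by at most 0.10 from its observed value. At the planning rate of 45%, that spans 35-55% for izokibep and never approaches a placebo-like 20%. The multiple imputation is the only planned ACR50 missing-data analysis that gives missing izokibep subjects values from a placebo model. If its rates are biased downward, part of any agreement with non-responder imputation is built in.

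**Working it through.** **Inputs from the documents.** ACR50 rule (SAP 2.4); predictor list (SAP 6.6.2); 20% placebo and 45% izokibep, 100 per arm (SAP 2.3).

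**Assumed inputs.** The documents give no correlations and no missing fraction. Assumed: correlation between components (ρ) 0.2-0.7; correlation over time within a component (τ) 0.3-0.85; 5-20% missing at Week 16.

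**1. The plan's own figure.** SAP 2.3 states 97% power. With mean rate 0.325:

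- null term: 1.96 × √(2 × 0.325 × 0.675 / 100) = 1.96 × 0.0662 = 0.1298
- SE of the difference: √(0.20 × 0.80/100 + 0.45 × 0.55/100) = 0.0638
- power: Φ[(0.25 − 0.1298) / 0.0638] = Φ(1.88) = 97.0%

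It reproduces. The plan gives no figure for the imputation itself.

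**2. How much correlation survives.** If each component is drawn from its own history with an independent residual, the correlation between two imputed components is R² × ρ, where R² is the share of variance explained by own history. With equal correlation τ between visits and k prior visits, R² = kτ² / (1 + (k − 1)τ). For ρ = 0.4:

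- no post-baseline visit: R² = 0, correlation 0
- one prior visit, τ = 0.5: 0.25 × 0.4 = 0.10
- three prior visits, τ = 0.5: (0.75/2) × 0.4 = 0.15
- three prior visits, τ = 0.7: (1.47/2.4) × 0.4 = 0.25

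Simulation gave the same values (0.00, 0.10, 0.15, 0.25). The correlation is attenuated, and lost completely only without post-baseline data.

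**3. Effect on imputed placebo ACR50.** Seven normal components at Weeks 2, 4, 12 and 16, with the response threshold set so that true Week 16 ACR50 is 20%. At ρ = 0.4, τ = 0.5:

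| Observed through | Imputed ACR50, SAP predictors |
|---|---|
| Baseline only | 8.5% |
| Week 2 | 11.7% |
| Week 4 | 12.6% |
| Week 12 | 13.2% |

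Across assumed ranges:

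| ρ | τ | No post-baseline visit | With history |
|---|---|---|---|
| 0.2-0.6 | 0.3-0.7 | 4.5-13.7% | 7.2-17.9% (through Week 12) |
| 0.3-0.7 | 0.5-0.85 | 3-11% | 7-18% (one prior visit) |

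In the first grid the rate fell in all 36 cases. Keeping same-visit correlation, with nothing else changed, restored 19.8-20.3%.

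**4. Does the baseline sentence rescue it?** With response defined as change from baseline and no post-baseline visit, own baseline only gave 6.2-13.8% and all seven baselines gave 6.3-13.5%. It does not.

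**5. Izokibep subjects with Week 12 data.** True rate 45%, placebo model applied to the subject's own history, ρ 0.3-0.7, τ 0.5-0.85.

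- Week 12 value alone as history, constant effect over visits: 17-39% with the SAP predictors against 31-41% under joint imputation, a shortfall of about 2-15 points.
- Weeks 2, 4 and 12 as history: 26-42% if the effect is constant; 17-30% if it builds up (assumed 30%, 50% and 85% of full effect at those visits). The shortfall is about 1-12 points.

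**6. Effect on the comparison.** Arm-level shift = missing fraction × shortfall. With 5-20% missing and shortfalls of 2-15 points, an arm's rate falls by 0.1 (0.05 × 2) to 3 points (0.20 × 15). With a 10-point shortfall in both arms and 15% versus 5% missing, the risk difference moves by 0.15 × 10 − 0.05 × 10 = 1.0 point. Against the SE of 6.4 points that is 1.0/6.4, or about 0.16 SE.

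**The case against.** The strongest reply is that this is one supplementary analysis and its effect on the comparison is small. All arms use the same placebo model, so shortfalls largely cancel when missingness and histories are similar. About 1 point against a planned difference of 25 will not change a conclusion. If more data are missing on izokibep, the error shrinks the difference and is conservative. All of this stands, and it limits the weight of the point.

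A reader might infer that the analysis imputes everyone somewhere between 0 and the placebo rate, and so merely repeats non-responder imputation. The documents do not support that. The model is fitted to placebo data but applied to each subject's own prior values. With Weeks 2, 4 and 12 as history, imputed izokibep rates exceeded 20% in 17 of 18 cases. Rates near zero arise mainly for subjects with no post-baseline data.

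A reader might also infer that each component is predicted from its own history alone. That is too strong: strata, sex, race, age, BMI and at least one baseline also enter. The covariates were not simulated and could restore a little correlation.

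Finally, MCMC in PROC MI is ordinarily a joint multivariate normal method, so the name could suggest joint draws. The explicit component-by-component predictor list and the sequential calls point the other way. The sample code cannot settle it, and the fallback applies only on non-convergence.

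**Conclusion.** The point holds in limited form. Followed as written, SAP 6.6.2 attenuates the correlation between ACR components and understates imputed ACR50 relative to a joint placebo-based imputation. The direction needs only positive correlation between components, which is assumed here. The sizes in steps 3 and 5 rest on assumed correlations, and step 6 also on assumed missingness. The result is a weaker robustness check, pulled part of the way toward non-responder imputation. The primary analysis, the tipping-point analysis and the alpha-controlled sequence do not use this model and are untouched. It should be corrected as a cheap improvement to a supplementary analysis; it does not threaten the trial's main conclusion.

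**What to change.** Impute the seven components jointly from placebo data, then derive ACR50. Keep the model small. All seven components at baseline and Weeks 2, 4 and 12 (7 × 4 = 28), six same-visit components and six covariates make 40 predictors for a Week 16 model fitted on about 100 placebo subjects, which risks unstable draws.

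A workable form is sequential or FCS regression using the component's own baseline and prior values (4), the same-visit values of the other components (up to 6) and the six covariates: at most 16 predictors at Week 16. Multivariate normal MCMC, with a ridge prior if needed, is an alternative.

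State whether own or all baselines enter, give the same predictor list for the FCS fallback, and replace the `var acr50` code with code that imputes the components. Make the change before unblinding so that the model is not chosen after seeing results.

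The cost is a few lines of text, modest programming and a slightly larger imputation model.
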